### 7.3 LOST TO FOLLOW-UP

A participant will be considered lost to follow-up if he or she fails to return for a visit within a 6 month time frame and is unable to be contacted by the study site staff.

The following actions will be taken if a participant fails to return to the clinic for a required study visit:

- The study coordinator will attempt to contact the participant and reschedule the missed visit within 2 weeks and counsel the participant on the importance of maintaining the assigned visit schedule and ascertain if the participant wishes to and/or should continue in the study.
- Before a participant is deemed lost to follow-up, the investigator or designee will make every effort to regain contact with the participant (3 telephone calls and, if necessary, a certified letter to the participant's last known mailing address). These contact attempts will be documented in the participant's medical record or study file.
- Should the participant continue to be unreachable, he or she will be considered to have withdrawn from the study with a primary reason of lost to follow-up.
- If a participant is reachable but is unable to come in person for the study visit, a telephone interview will be conducted with the participant and an informant to assess the secondary end point of dementia / MCI.

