## 8 STUDY ASSESSMENTS AND PROCEDURES

### 8.1 EFFICACY ASSESSMENTS

#### **Screening assessment**

Screening for eligible participants will be performed using the Mayo medical records by a study coordinator. Only patients who have previously given consent to the use of their medical records for research purposes will be screened. ECG, Holter, telemetry recordings will be reviewed to confirm the diagnosis of AF. Charts will be reviewed to assess eligibility for the study including past medical history, current medications, laboratory tests and calculation of the CHA2DS2-VaSC score. The creatinine will be checked if a measurement within 3 months of enrollment is not available.

Potential participants will be contacted in person or through a letter or on the phone. Interested persons will be interviewed on the phone to confirm eligibility and will have a blood test for creatinine if needed. Once enrolled, subjects will be randomized to one of the study arms and will start study drug.

Baseline assessment of brain MRI will be performed prior to initiation of study drug. Baseline assessment of cognitive function will be performed prior to or within 1 month of enrollment. Subsequent assessments will be performed at 1 and 2 year follow-up or within a 3 month time frame of this date.

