### ***Measurement of secondary endpoint: Mild cognitive impairment or dementia***

The CDR score (range 0–3) will be assessed in addition to the results of the neuropsychological testing. A team of Neurologist and Neuropsychometrist will assign a diagnosis of normal cognition or mild cognitive impairment or dementia to each subject at each time point. This team will be blinded to treatment assignments. Each assessment of an individual patient will be assessed independent of prior assessments. The definitions used are as follows:

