## **8.2 SAFETY AND OTHER ASSESSMENTS**

1. Assessment for adverse events will be performed on an ongoing basis and at each patient visit.
2. At each study visit, the participant will be interviewed by the study coordinator to assess for adverse events. The medical records will be reviewed on an ongoing basis to identify occurrence of adverse events and hospitalizations.
3. Occurrence of medical events and addition of drugs that may affect continued eligibility for the study will be assessed at each visit. The age, creatinine and patient weight will be assessed at each patient visit to assess appropriateness of drug dosing.
4. The brain MRI will be screened for adverse events such as identification of asymptomatic intracranial bleeding after each assessment.

Definitions for a selection of important adverse events:

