#### Testing of four major cognitive function domains

5. Executive function - Trail Making Test B and Digit Symbol Substitution Test
6. Language - Boston Naming Test and Category Fluency
7. Memory - Logical Memory-II (delayed recall), Visual Reproduction-II (delayed recall) and Auditory Verbal Learning Test (delayed recall)
8. Visuospatial - Picture Completion and Block Design

Questionnaires to rule out competing diagnoses:

1. The Beck Depression Inventory
2. The Beck Anxiety Inventory

An informant, identified by the subject as someone with whom they have contact at least once every week, will be interviewed in person or by telephone to complete the following:

1. Clinical dementia rating scale (CDR)
2. Functional assessment questionnaire

For patients lost to clinic follow-up, assessment of cognitive state will be performed using the following questionnaires administered over the telephone:

Telephone interview of cognitive status (TICS-M) (administered to subject)

2. Clinical dementia rating scale (administered to informant)
3. Functional assessment questionnaire (administered to informant)

Patients who no longer present for in person neurocognitive assessment will be censored from the analysis of the primary endpoint of neurocognitive function scores. The telephone interview will be used to classify as MCI / dementia and the data will be used for this secondary endpoint only.

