### 9.4 STATISTICAL ANALYSES

#### 9.4.1 GENERAL APPROACH

Continuous and categorical variables will be summarized as mean (standard deviation, SD) and number (%) respectively. Differences between the two treatment arms at baseline will be examined using t-tests for continuous variables and chi-square tests for categorical variables.

The baseline variables include age, sex, education, cardiovascular risk factors (hypertension, diabetes mellitus, hyperlipidemia), past medical history (including stroke, TIA, heart failure, peripheral arterial disease, MI, coronary artery disease, liver disease, renal disease, malignancy), duration of AF, pattern of AF (paroxysmal, persistent), prior h/o anticoagulation (duration and type of drug used), prior treatment of AF (antiarrhythmic drug, ablation procedure), and current medications. This data will be reviewed and updated at each visit. The INR values during the study will be collected for patients on warfarin and the time in therapeutic range calculated using the Rosendaal method of interpolation.

Longitudinal changes in each cognitive domain (language, attention, memory, visual spatial and global) will be analyzed using multiple adjusted linear mixed effects models comparing Apixaban vs warfarin. These models will be adjusted for baseline variables that differ between the groups. These results will be presented as beta estimates for baseline differences in cognitive function score by treatment status, change with time and the effect of treatment on the change in scores over time.

For the secondary end point of dementia/MCI, the mid-point between the most recent visit with a cognitively normal diagnosis and the first visit with a diagnosis of MCI or dementia will be considered the date of onset. Participants who are lost to follow-up or die during follow-up will be censored at the

date of last follow-up. Cox proportional hazards model will be used to assess the secondary end points of MCI/dementia, cerebral infarction and cerebral microbleeds. Adjustment for baseline factors noted above will be performed in the multivariable model.

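### The MCI/dementia censoring date is undefined and may fall after the last cognitive classification, so unassessed time can count as event-free

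*Combined protocol and SAP*

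**What the plan says.** **Diagnosis.** Under section 8.1, a blinded team "will assign a diagnosis of normal cognition or mild cognitive impairment or dementia to each subject at each time point". After baseline, "Subsequent assessments will be performed at 1 and 2 year follow-up or within a 3 month time frame of this date".

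**Event date.** Section 9.4.1 places onset at "the mid-point between the most recent visit with a cognitively normal diagnosis and the first visit with a diagnosis of MCI or dementia". With yearly visits that is about 0.5 or 1.5 years.

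**Censoring.** Section 9.4.1 continues: "Participants who are lost to follow-up or die during follow-up will be censored at the" date of last follow-up. It does not say whether this is the last visit, the last contact or the date of death. Section 7.1 gives another rule: those who withdraw or change anticoagulant are censored when they withdraw. Section 7.3 classes patients who stay unreachable as withdrawn, after a missed visit, a 6-month time frame and repeated contact attempts.

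**Model.** "Cox proportional hazards model will be used to assess the secondary end points of MCI/dementia, cerebral infarction and cerebral microbleeds".

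**Safeguards.** Section 7.1 requires cognitive testing at withdrawal if more than 6 months have passed since the last assessment; otherwise the last assessment is used. For patients who can be reached but cannot attend, section 7.3 says that "a telephone interview will be conducted with the participant and an informant to assess the secondary end point of dementia / MCI", and section 9.1 adds: "The telephone interview will be used to classify as MCI / dementia and the data will be used for this secondary endpoint only".

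**The concern.** Events and non-events are dated by different clocks. An event exists only if a later classification was made, and it is then moved back to the middle of the interval. A non-event may be carried forward to a date at which no classification was made.

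Take a patient who is normal at year 1, misses the year-2 visit and cannot be reached. Sections 7.1 and 7.3 together censor this patient at the declared withdrawal, which can fall after the missed visit. The patient then sits in the Cox risk set at 1.5 years as if known to be event-free, although nobody assessed cognition after year 1. A patient who dies at 1.9 years is treated the same way if the date of last follow-up is read as the death or a late contact.

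Such patients enlarge the denominator at the mid-point but can never enter the numerator. Each arm's incidence is understated, by more where more patients are lost in this way. If that loss differs between arms, the hazard ratio moves in favour of the arm with more of it.

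**Working it through.** **The plan's own figures.** The plan gives no rate, event count or power for MCI/dementia. Section 9.2 sizes only the primary endpoint: 0.05 / (0.16 × √(2/140)) = 2.61, and Φ(2.61 − 1.645) = 0.834, which agrees with the stated power above 80% at 140 per arm. That figure does not bear on this endpoint.

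**Inputs.** From the documents: visits at 1 and 2 years with a 3-month window, mid-point event dates, a Cox model and 1:1 allocation. Assumed: yearly loss *d* of 5% to 15%, and onset of 5% to 15% per year.

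**Formula.** Let *h* be the true risk in a yearly interval, with a fraction *d* lost evenly over it and unrelated to onset. Only the 1 − *d* who reach the visit can become events. At the mid-point half of the losses have left, so 1 − *d*/2 are at risk.

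- Censored at the date of loss: apparent risk = (1 − *d*)*h* / (1 − *d*/2).
- Censored at the last classification: apparent risk = (1 − *d*)*h* / (1 − *d*) = *h*.

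**Numbers, no exit testing, true hazard ratio 1.** Fraction of true risk seen:

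- *d* = 5%: 0.95/0.975 = 0.974
- *d* = 10%: 0.90/0.95 = 0.947, so incidence is about 5% too low
- *d* = 15%: 0.85/0.925 = 0.919, so incidence is about 8% too low

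Ratio, lower-loss over higher-loss arm:

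- 10% v 5%: 0.974/0.947 = 1.03
- 15% v 5%: 0.974/0.919 = 1.06
- equal loss: 1.00

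**Simulation.** With 1,000,000 patients per arm, visits within the 3-month window and onset of 5%, 10% or 15% per year, a two-group Cox model gave 1.02 to 1.03 for 10% v 5% and 1.05 to 1.06 for 15% v 5% when patients were censored at the date of loss. Censoring at the last classification gave about 1.00. The onset rate made little difference.

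**Exit testing.** With yearly visits the event mid-point falls about 6 months after the last classification. A patient who withdraws sooner is censored before it and does no harm; one who withdraws later is due for testing under section 7.1. In a simulation with 10% yearly onset, testing half of the losses gave 1.02 (10% v 5%) and 1.03 (15% v 5%). Testing all of them gave about 1.01.

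**Late declaration of loss.** If every loss were an unreachable patient censored only after the missed visit, all would still be at risk at the mid-point and the apparent risk would be (1 − *d*)*h*. The ratio would be 0.95/0.90 = 1.06 for 10% v 5% and 0.95/0.85 = 1.12 for 15% v 5%. This is an extreme case, since it allows no ordinary withdrawals or deaths.

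**Loss related to onset.** If the loss hazard doubles after onset, censoring at the date of loss gives about 1.05 (10% v 5%) and 1.11 (15% v 5%). Censoring at the last classification gives about 1.02 and 1.05, so about half of the bias remains.

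**Effect on a test.** Assume 10% yearly onset and no loss: 280 × (1 − e^−0.2) ≈ 51 events, taken as 50. Then SE(log HR) = 2/√50 = 0.28. A null ratio of 0.95 (higher-loss over lower-loss) shifts the statistic by 0.051/0.28 = 0.18. One-sided 5% error in favour of the higher-loss arm becomes about 7.2%; two-sided 5% error becomes about 5.4%.

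**The case against.** The strongest reply is that the plan may already intend the right thing. Section 8.1 uses follow-up for the scheduled 1- and 2-year visits. On that usage the date of last follow-up is normally the last diagnosis, and the problem disappears for section 9.4.1. A reader might infer that censoring at last contact is settled, because "The medical records will be reviewed on an ongoing basis to identify occurrence of adverse events and hospitalizations" (section 8.2). Nothing links that review to the censoring date, so the documents do not support this. What stands is narrower: the term is undefined, and sections 7.1 and 7.3 do use the withdrawal date.

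The second reply is that exit testing and telephone classification close much of the gap. They do, and diagnosis is not confined to clinic visits. Neither can cover patients who die or cannot be reached, the two groups that the section 9.4.1 sentence concerns, and some patients will refuse exit testing.

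The third reply is that the loss differences are assumed and the endpoint is secondary and unpowered. Both points are fair, and they limit the weight of the finding.

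A reader might also infer that the error works against apixaban, since section 2.3.2 cites lower mortality on that drug. That section gives only a p-value for all-cause death, with no rates. An assumed 4% v 3% yearly mortality gives (0.97/0.985) / (0.96/0.98) = 1.005. Withdrawal and switching also count as loss. The open-label design, the free supply of apixaban only, and withdrawal on changing anticoagulant make unequal loss plausible, but its direction cannot be told.

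**Conclusion.** The concern holds in a limited form. The censoring date is undefined in section 9.4.1, and sections 7.1 and 7.3 together credit unreachable patients with time in which they were not assessed. Whether deaths are affected depends on how the undefined term is read.

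For assumed loss differences of 5 to 10 points a year and loss unrelated to onset, the null ratio moves to about 1.03 to 1.06 without exit testing and about 1.01 to 1.03 with it. These figures take censoring to fall at the date of loss. With equal loss the hazard ratio is unbiased, although each arm's incidence is still too low. The documents do not show which arm would benefit.

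Censoring at the last classification might be taken as a complete cure. It restores 1.00 only if loss is unrelated to onset, and a patient who develops MCI and dies before the next classification is still never counted.

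**What to change.** In section 9.4.1, and in the same terms in section 7.1, state: *Participants without MCI or dementia are censored at the date of their last in-person or telephone cognitive classification, whatever the date of death, withdrawal or last contact.* Say also how section 7.3 losses fit this rule, and whether it covers only MCI/dementia, since the same Cox model is named for infarcts and microbleeds.

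Preferably replace the mid-point Cox model with a grouped-time model (complementary log-log link, intervals 0–1 and 1–2 years) or an interval-censored model, so that only classified intervals contribute. Add a sensitivity analysis with death as a competing event, and report loss by arm and reason, because the censoring change does not deal with loss related to onset.

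The cost is a few sentences and slightly less person-time: patients with no classification after baseline contribute none. No new data are needed. The rule should be fixed before outcomes are seen by arm, so that the choice of date cannot appear driven by the result.

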Participants who change OAC treatment during follow-up will be withdrawn from the study. A CRF will collect details of the reason for discontinuation of study intervention. Endpoints will be assessed at the time of withdrawal from the study including MRI and cognitive function. The MRI of the head and / or cognitive assessment will be performed at the time of withdrawal from the study if it is greater than 6 months since their last assessment of MRI and / or cognitive function. If a patient withdraws within 6 months of the last assessment, repeat testing will not be performed and the last assessment will be used for the analysis. Participants who withdraw from the study will be followed for 30 days after withdrawal for adverse events. A primary intention to treat analysis will be performed at the end of the study. Participants who withdraw or change OAC treatment will be censored at the time of withdrawal.

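### New MRI lesions are detected at a single follow-up scan, but the Cox analysis of them has no onset or censoring rule tied to that scan

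*Combined protocol and SAP*

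**What the plan says.** **Scan schedule.** Sections 3, 4.1 and 8.1 schedule brain MRI at baseline and 2 years. Section 8.1 allows follow-up assessments a 3-month window. Section 7.1 adds a scan at withdrawal if more than 6 months have passed since the last one: "Endpoints will be assessed at the time of withdrawal from the study including MRI and cognitive function". The participant then leaves the study, so the exit scan replaces the 2-year scan. Nobody has more than one follow-up MRI under the protocol.

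**Model.** Section 9.4.1: "Cox proportional hazards model will be used to assess the secondary end points of MCI/dementia, cerebral infarction and cerebral microbleeds".

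**Onset date.** The same section gives one rule, which takes the half-way date between two visits: "For the secondary end point of dementia/MCI, the mid-point between the most recent visit with a cognitively normal diagnosis". The later end of the interval is the visit at which impairment is first diagnosed. The rule is introduced for dementia/MCI and is not extended to MRI lesions.

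**Censoring.** Two rules exist. Section 9.4.1 censors at the last follow-up date (the quote stops just short of it): "Participants who are lost to follow-up or die during follow-up will be censored at the". This rule follows the dementia/MCI sentence, and its scope is not stated. Section 7.1: "Participants who withdraw or change OAC treatment will be censored at the time of withdrawal"; this is not limited to any endpoint. Neither mentions the scan.

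**Participants who stop attending.** Section 7.3 provides that "a telephone interview will be conducted with the participant and an informant to assess the secondary end point of dementia / MCI". For these people Section 9.1 settles the cognitive score ("Patients who no longer present for in person neurocognitive assessment will be censored from the analysis of the primary endpoint") and the diagnosis ("The telephone interview will be used to classify as MCI / dementia and the data will be used for this secondary endpoint only"). It does not mention MRI.

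**Microbleed sequence.** Section 3 names SWAN. Section 8.1 names GRE and MPRAGE for quantifying microbleeds, although it also lists SWAN among the sequences acquired.

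**The concern.** A Cox model needs an event or censoring time for each person. Here the data are an interval (baseline to the single follow-up scan) and a yes/no answer. The plan handles this structure for dementia/MCI with the mid-point rule and leaves it open for MRI, so the analyst must choose the event date, the coding of visit time, the tie method, and what to do with people who were never rescanned.

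These choices affect the result. If everyone is dated at their own scan, lesion-free participants leave the risk set at much the same times as events occur. The model then estimates roughly the ratio of lesion-positive proportions instead of the hazard ratio. If more people leave early in one arm, their lesions are dated early simply because they were scanned early, and that arm appears to have the higher rate. Unequal withdrawal is possible: the trial is open-label, a change of anticoagulant means withdrawal (Section 7.1), and only apixaban is supplied free (Section 2.3.1). The documents give no withdrawal rates.

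The MRI endpoints matter because they test the proposed mechanism, namely that fewer infarcts and microbleeds explain slower cognitive decline.

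**Working it through.** **The plan's figures.** Section 9.2 gives power for the primary endpoint only: difference 0.05/year, SD 0.16, 140 per arm, one-sided 0.05. The standard error is 0.16 × √(2/140) = 0.0191, and 0.05/0.0191 = 2.61. Power is Φ(2.61 − 1.645) = 83.4%, which agrees with the stated >80%. No lesion risk, power, alpha or sidedness is given for the MRI endpoints.

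**Inputs.** From the documents: 140 per arm, 1:1 allocation, and 2-year scans at 21-27 months. Assumed: lesion risk 30% on warfarin v 20% on apixaban, constant lesion rate, two-sided 5%.

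**What each dating estimates**
- Constant rates give a true hazard ratio of ln(0.8)/ln(0.7) = 0.626.
- Dating at the individual scan gives about 0.20/0.30 = 0.667.

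**Closed-form power.** Expected events are 140 × 0.30 + 140 × 0.20 = 70. By the Schoenfeld formula, z = |ln HR| × √70/2.
- Scan-dated: 0.405 × 4.183 = 1.696. Power Φ(1.696 − 1.960) = 39.6% two-sided, and Φ(1.696 − 1.645) = 52% one-sided.
- Interval-based: 0.469 × 4.183 = 1.962. Power Φ(1.962 − 1.960) = 50% two-sided, and Φ(1.962 − 1.645) = 62% one-sided.

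**Simulation, no withdrawal, two-sided 5%.** Ranges cover separate runs.

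| Analysis, 30% v 20% | HR | Power |
|---|---|---|
| Cox, actual scan dates | 0.66 | about 38-40% |
| Cox, mid-point event, lesion-free censored at scan | 0.62 | about 48-50% |
| Complementary log-log | 0.62 | 48.5-49.6% |
| Cox, all scans coded month 24, Efron ties | 0.62 | 48.4-49.9% |
| Cox, all scans coded month 24, Breslow ties | 0.66 | about 37-38% |

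**Dependence on the assumed risk** (same risk ratio; actual-date Cox v complementary log-log)

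| Risk | Power |
|---|---|
| 40% v 26.7% | 47.8% v 65.9% |
| 30% v 20% | 38.0% v 48.5% |
| 20% v 13.3% | 26.3% v 31.6% |
| 10% v 6.7% | 14.1% v 15.3% |

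**Unequal withdrawal, no true effect.** Assumed: 30% risk in both arms; withdrawal 25% warfarin v 10% apixaban, uniform over months 6-21, each with an exit scan that counts.
- Scan-date Cox with Efron ties: HR about 0.88-0.89, whether the 2-year scans are coded at actual dates or month 24. With actual dates, one run rejected in 7.8% of trials.
- Mid-point Cox and complementary log-log: HR about 0.98-1.00, rejection about 5%.
- Scale: ln(0.894) = −0.112, against a log-HR standard error of 0.231, so about half a standard error (0.112/0.231 = 0.48).
- With equal withdrawal, scan-date Cox gives 1.00.

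**The case against.** Several stronger readings are tempting, and the documents do not support them.

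*The plan has no censoring rule for MRI.* Section 7.1 has a general rule, and the one in Section 9.4.1 stands directly before the Cox sentence. What is missing is a rule tied to the scan.

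*Dating at the scan always costs about 10 points of power.* It does not. Coding all scans at one nominal time with Efron ties removes the loss, and low lesion risks make it negligible. Extending the plan's own mid-point rule also removes it. What stands is that the plan fixes neither date coding nor tie method, so power of 38% or 48% can depend on a choice made after the data exist. The direction does not depend on sidedness: one-sided, the contrast is about 51-52% v 62%.

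*People followed by telephone will be counted as lesion-free.* This is the worst reading. Section 9.1 restricts telephone data to MCI/dementia, and Section 7.3 separates reachable participants from those lost. If the unscanned are 15% v 5% by arm with no true effect, censoring them at 21-27 months gives hazard ratios of 1.12-1.14; censoring at the 1-year visit gives 1.00 (scan-date) or 1.08 (mid-point). The remaining gap is that no rule is stated.

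*Exit-scan lesions are discarded.* Section 7.1 orders endpoint assessment at exit, so counting them is the natural reading. It should still be stated, because the same section censors at withdrawal. When someone withdraws in the first 6 months, the assessment reused is the baseline MRI, which cannot show a new lesion.

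*Blinded reading and age/sex adjustment are missing.* Both are present, in Sections 4.1, 6.3 and 8.1 and in Section 9.4.1 respectively.

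It is also fair to say that the complementary log-log model has no real advantage in power over mid-point Cox. Either would do.

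**Conclusion.** The point holds as a gap in specification with a cheap remedy. The plan applies a time-to-event model to data with one follow-up look, and it leaves the event date and scan-based censoring undefined for MRI.

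Under assumed risks of 30% v 20%, actual scan dates and a two-sided 5% test, the cost is about 10 points of power. It is about 1 point at 10% v 6.7% and zero under one particular coding. Under assumed withdrawal of 25% v 10% and no true effect, scan-date Cox moves the hazard ratio to about 0.88-0.89 in apixaban's favour under both date codings tried with Efron ties, while the interval-based analyses stay near 1.00. That shift is below the sampling error of a single trial. Every lesion and withdrawal rate here is an assumption, because the documents supply none.

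The endpoints are called secondary in the synopsis and Sections 4.1 and 9.1, and tertiary in Section 3. A reader should not infer that the primary cognitive analysis is affected; it is not.

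**What to change.** In Section 9.4.1:
- Analyse new infarct and new microbleed with a complementary log-log (interval-censored) model with log(scan interval) as offset. Alternatively, keep Cox, extend the mid-point rule explicitly to MRI, and censor lesion-free participants at their last MRI.
- Treat participants with no follow-up MRI as missing for these endpoints, not lesion-free, and add a sensitivity analysis for missing scans.

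In Section 7.1, state that a lesion on an exit scan counts as an event.

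Reconcile Sections 3 and 8.1 so that one microbleed sequence is named and used at both scans.

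**Cost.** Wording and slightly more analysis work, with no additional scans. The complementary log-log model assumes roughly constant lesion rates and withdrawal unrelated to lesions, which is why the sensitivity analysis is needed. Treating unscanned participants as missing reduces the number analysed.

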## 5.5 STRATEGIES FOR RECRUITMENT AND RETENTION

1. This is a single center study that will be conducted at the Mayo Clinic, Rochester, MN. Target study sample is total of 280 patients. Assuming a screen failure rate of 20%, target accrual is 350 participants. Accrual will be completed in 1 year. The last patient will complete follow-up 2 years later.
2. In order to enrich the study for the population at risk of the primary end point, at least 50% of the enrollees will be >70 y of age.
3. Participants will be identified using two strategies: (1) Individuals with AF living in the 8 counties of Southeast Minnesota (Dodge, Fillmore, Goodhue, Houston, Olmsted, Mower, Wabasha and Winona counties) will be screened for eligibility. Such patients will be identified using the record linkage system of the Rochester Epidemiology Project and Mayo Clinic, Rochester clinical records. Potential participants with AF diagnosed in Olmsted county have already been identified through prior work the investigators have done. (2) Individuals seen in the inpatient and outpatient clinics at Mayo Clinic, Rochester, MN with a diagnosis of AF will also be screened for eligibility. Such patients will be identified by the treating physician, using screening of their medical records and through the Mayo ECG laboratory which flags patients with new identification of AF.
4. Potential participants will be approached using one or more of the following: (1) direct patient contact in the clinic or hospital, (2) through letters and (3) phone calls.
5. The ECG documentation of AF will be confirmed using review of the medical records. Eligibility for the study will be determined first using medical records and confirmed by direct interview of the patient prior to enrollment.
6. Participants will be compensated for their participation in the study as follows: (1) each participant will be given \$15 at the time of each neurocognitive assessment and (2) a Mayo parking voucher at the time of each MRI assessment. The compensation is intended to encourage patients to continue study related tests by providing partial compensation for travel expenses.

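### The covariates for the three secondary Cox models are not a short set fixed in advance; read literally they are at least 22 terms, more than any plausible number of MCI/dementia events can support

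*Combined protocol and SAP*

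**What the plan says.** The rule is in Section 9.4.1 of the combined protocol and SAP. One sentence sets the model for all three endpoints: "Cox proportional hazards model will be used to assess the secondary end points of MCI/dementia, cerebral infarction and cerebral microbleeds". The next sets the covariates: "Adjustment for baseline factors noted above will be performed in the multivariable model".

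The list that this appears to point to is earlier in the same section. It opens with demographic items and three risk factors: "The baseline variables include age, sex, education, cardiovascular risk factors (hypertension, diabetes mellitus, hyperlipidemia". It goes on to nine named diagnoses, introduced in a way that leaves room for more, and then to the history of the arrhythmia and of earlier anticoagulant use (four items). It closes with "prior treatment of AF (antiarrhythmic drug, ablation procedure), and current medications".

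Between the list and the Cox sentence, the section gives a different rule for the mixed models of cognitive scores: they adjust only for baseline variables on which the two arms differ. The Cox sentence does not say which of the two it refers to.

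On trial size, Section 5.5 says "Target study sample is total of 280 patients". Section 4.1 sets 2 years of treatment, with cognitive testing at 0, 1 and 2 years and MRI at 0 and 2 years. Section 9.2 sizes the trial on the global cognitive score alone. No section gives an expected event count, a covariate selection rule, penalisation or a power check for the Cox models.

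**The concern.** A Cox model draws its information from events, not patients. A model with about as many terms as events, or more, fits noise: coefficients of rare covariates can diverge, the treatment log hazard ratio becomes more variable, and it tends to drift away from the null. Randomisation already protects the treatment comparison from baseline confounding, so a long list buys little in return.

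The other reading has its own fault. If the covariates are those that differ between arms, they are chosen by baseline significance tests after the data are seen, and nobody can say beforehand which model will be fitted. Randomisation is stratified by age decade and sex, so those two factors will seldom differ between arms. This rule would therefore tend to leave out the factors with the best claim to be in the model.

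At stake are the three secondary hazard ratios. The primary analysis has its own rule and is not affected by this sentence.

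**Working it through.** **1. The plan's own figure.** Section 9.2 gives 140 per arm, a difference of 0.05/year, SD 0.16, and one-sided alpha 0.05. The standard error is 0.16 × √(2/140) = 0.0191, and 0.05/0.0191 = 2.61. Power is Φ(2.61 − 1.645) = 0.83, which agrees with the stated figure of more than 80%. Accrual of 140/0.80 = 175 per arm also agrees. This calculation concerns a difference in mean slopes and says nothing about event counts.

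**2. Terms under the literal reading,** counting each named item once:

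| Group | Terms | Running total |
|---|---|---|
| Age, sex, education, three risk factors | 6 | 6 |
| Medical history | 9 | 15 |
| AF duration and pattern; prior anticoagulant duration and type | 4 | 19 |
| Antiarrhythmic drug, ablation, current medications | 3 | 22 |

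This is a minimum. The history list is open-ended, and drug type and current medications can each need several terms. Treatment makes 23.

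**3. Events.** The annual MCI/dementia rate r is not in the documents, so it is assumed. Events = N × (1 − e^(−2r)). N = 280 is the full sample. N = 200 is an assumed lower figure: Section 5.2 excludes dementia but not MCI at baseline, and Section 7.1 censors patients who withdraw or change anticoagulant.

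| r per year | Events, N = 280 | Events, N = 200 |
|---|---|---|
| 2% | 11 | 8 |
| 3% | 16 | 12 |
| 5% | 27 | 19 |
| 7% | 37 | 26 |
| 10% | 51 | 36 |
| 15% | 73 | 52 |

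Events per listed term run from 7.84/22 = 0.36 to 72.6/22 = 3.3. Five per term would need 110 events, an annual rate of −ln(1 − 110/280)/2 = 25%.

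**4. Imprecision that exists without any adjustment.** The standard error of the log hazard ratio is about 2/√events: 0.52 at 15 events and 0.33 at 36. The 95% interval therefore spans a factor of e^(1.96 × 0.516) = 2.75 each way at 15 events, and 1.92 at 36.

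**5. What the long list adds.** These are simulations of 280 patients with 22-23 covariates of the listed kinds. Event rates and covariate prevalences are assumed. The comparison is with treatment, age and sex only.

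| Events (about) | SD of log HR, full list | SD, treatment + age + sex | Ratio |
|---|---|---|---|
| 17 | 0.70 | 0.53 | 1.32 |
| 25 | 0.56 | 0.43 | 1.30 |
| 38 | 0.39 | 0.32 | 1.22 |

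Other assumed settings gave ratios of 0.66/0.49 = 1.35 at about 20 events, 0.56/0.45 = 1.24 at 23, 0.47/0.37 = 1.27 at 33 and 0.39/0.33 = 1.18 at 36. The smallest, using an interquartile-based SD for the full list, was 0.39/0.36 = 1.08 at 36. Most lie between about 1.2 and 1.35.

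*Drift.* At about 20 events and a true log HR of −0.51 (HR 0.60), the mean estimate was −0.66 (HR 0.52) with the full list and −0.52 (HR 0.59) with the short set. With a true HR of 0.70, the median full-list HR was 0.64, 0.66 and 0.68 at 15, 25 and 36 events.

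*Failed fits.* With about 15-38 events, there was no usable treatment estimate in 0-14% of trials. The result is sensitive to the setting: one gave 12% at about 23 events, another none at 20 or more.

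**6. The other reading.** If variables are chosen by the planned t-tests and chi-square tests at an assumed 5% level, 22 × 0.05 = 1.1 would be chosen by chance. Treating the tests as independent, three or fewer would be chosen in about 98% of trials. That model is not overloaded, but its contents are unknown until the data are seen.

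**The case against.** The strongest reply is that the sentence may not mean the full list. The nearer antecedent is the rule in the preceding paragraph, and under it the events-per-term problem disappears (step 6). This stands as a point about ambiguity. It does not rescue the plan, because it replaces an overloaded model with one chosen by significance tests.

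A second reply is that few events, not the covariates, cause most of the imprecision. This is correct: step 4 shows wide intervals without any adjustment, and the fix will not narrow those. Section 9.4.1 also does not say that the adjusted model is the only one to be reported, so an unadjusted result may stand beside it. And because withdrawals and changes of anticoagulant are censored, prognostic covariates may have some role beyond what randomisation provides. That supports keeping a few strong ones, not all 22.

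Three stronger readings are tempting and are not supported:

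- *Post-randomisation values will enter the models.* A reader might infer this from "This data will be reviewed and updated at each visit", since the list includes stroke, TIA and current medications. But that sentence describes data collection, and the adjustment sentence says baseline factors. Nothing says that updated values are used.
- *The type I error is inflated.* Simulated two-sided rates with the full list were 6.4-7.6%. With 250 runs, the Monte Carlo interval around 7.6% is 7.6 ± 1.96 × √(0.076 × 0.924/250) = 4.3% to 10.9%, which includes 5%. Inflation is not clearly shown.
- *The treatment hazard ratio cannot be estimated.* Divergence is common for at least one covariate coefficient, but the treatment estimate is usually obtained.

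**Conclusion.** The concern holds in this form. Section 9.4.1 does not fix a short covariate set for the secondary Cox models. On the literal reading it prescribes at least 22 terms for an assumed 8-73 MCI/dementia events, or about 0.36-3.3 per term. That the list is too long does not depend on the exact rate within the 2-15% per year considered.

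The cost to the treatment estimate is real but moderate. At about 15-38 events, its SD is roughly 20-35% larger than with treatment, age and sex only, there is modest drift away from the null when an effect exists, and a minority of trials (0-14%) give no usable estimate. These sizes rest on assumed event rates and covariate prevalences; the documents supply neither.

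For infarcts and microbleeds the same rule applies, but no size can be given. A reader might take the figure of up to 90% for ischemic lesions in Section 2.2 as an event rate. It is the share of AF patients reported to have such lesions, not the rate of new ones.

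This should be corrected before the secondary analyses are run. It does not affect the primary endpoint.

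**What to change.** Replace the adjustment sentence in Section 9.4.1 with:

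*Each secondary model contains treatment and the randomisation factors (age decade and sex), and may include one pre-specified baseline measure of that outcome, all at values recorded before randomisation. Any wider covariate set is a labelled sensitivity analysis, with penalised likelihood.*

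If a baseline outcome measure is used, name it for each endpoint. State the expected number of events for each of the three endpoints and the source of the rate, or say that none is available. Specifying values recorded before randomisation also settles any doubt about updated data.

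The cost is SAP wording only, with no change to data collection or sample size. The downside is that the fully adjusted model is no longer a main secondary result. The wide intervals that come from few events will remain.
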